***“Innovative immune monitoring in a clinical trial of radiotherapy and immune checkpoint blockade”***

**PROTOCOL SYNOPSIS**

[figure not shown]
[figure not shown]
Protocol Title	Radiation and immune checkpoints blockade in metastatic NSCLC
Sites	Weill Cornell Medicine – New York Presbyterian Columbia University, New York Presbyterian

Study Schema	
Metastatic NSCLC patients with a minimum of two metastatic lesions (at least one measurable) are eligible if they have an ECOG Performance Status of 0-1. Patients must be willing to undergo a required pre-treatment biopsy prior to enrolling onto the study.
 
Non-ablative radiotherapy (6GyX5) is directed to one lesion on day 1 with ipilimumab 3 mg/kg (<math>\pm</math> 24hrs from first RT dose). On day 22 the combined treatment of ipilimumab plus nivolumab will start (nivolumab 360mg q 3 weeks, ipilimumab 1mg/kg q 6 weeks), and administered until evidence of progression. Patients are re-imaged at Week 9 (day 70 <math>\pm</math> 7) to evaluate for response (defined as an objective response by RECIST of the measurable metastatic sites outside the radiation field). This response will be evaluated assessing clinical and PET/CT responses in the non-irradiated measurable metastatic sites using RECIST 1.1.

Trial Objectives	
Primary Objectives:
 
To enhance the ORR to the combination of Ipi/Nivo in metastatic NSCLC by preceding it with a combination of Ipi/RT to convert the irradiated tumor into an in situ vaccine
 
Secondary objectives:
 
To explore whether early changes in TCR repertoire in peripheral blood are associated with response to treatment
 
To explore if serum markers levels/changes are associated with response
 
To explore associations of ORR with changes in the microbiome
 
Progression Free survival and Overall Survival (OS)
 
Time to progression and Duration of response (DOR)

Study Design	
A Simon's two-stage optimal design is chosen for this trial. Fifteen patients are required for stage 1. If 5 or more responses are seen, then the trial will proceed to stage 2 and an additional 29 patients will be enrolled and treated. If a total of <math>\geq</math> 18 objective responses are demonstrated the trial will achieve its main endpoint. We expect to accrue up to a total of 48 patients, independently from their PD-L1 status.

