#### 4.0 STUDY DESIGN

A Simon's two-stage optimal design is chosen for this trial, thus 15 patients are required for stage 1. If 5 or more responses are seen then the trial will proceed to stage 2 and an additional 29 patients will be enrolled and treated. If a total of  $\geq 18$  objective responses are demonstrated the trial will achieve its main endpoint.

We expect to accrue up to a total of 48 patients, independently from their PD-L1 status.

**Objective 2.1:** To demonstrate safety of combining initial concurrent radiotherapy and Ipilimumab as an induction regimen to the combination of Ipi/Nivo in NSCLC

A Simon's two stage design study of combined RT and Ipi (RT-Ipi), followed by maintenance of ipi/nivo is proposed for patients with metastatic NSCLC. Bristol-Myers Squibb (BMS) will provide drug and study support (ipilimumab and nivolumab) to patients on study (see letter of commitment from BMS).

Eligibility criteria: Patients  $>18$  years of age with histologically proven metastatic NSCLC, at least two measurable sites of disease, adequate organ and bone marrow function, ECOG PS 0-1 or Karnofsky  $\geq 70\%$  and informed consent for participation. Systemic or local anti-cancer therapies must be completed at least 2 weeks before the start of treatment. Baseline PET/CT or CT (chest, abdomen, and pelvis) is required within 4 weeks from accrual.

Treatment: At study entry all measurable metastatic lesions identified clinically or at PET/CT are recorded. Choice of the metastasis to be biopsied before and after RT-Ipi is based on ease of access (lymph nodes and subcutaneous metastases are preferred) and the estimated lowest risk for complications associated with tissue acquisition. The treatment starts a week after biopsy (during this week patients undergo CT simulation for radiation therapy). A regimen of 6 Gy X 5 daily fractions will be delivered to the biopsied lesion. Patients will receive ipi 3 mg/kg i.v. over 30 minutes initiated within 24 hours of the first dose of RT to the biopsied measurable lesion, conformally or by IMRT, with image guidance, to maximally spare normal tissue. At day 22 patients are started on the ICB combination of nivolumab 360 mg q 3 weeks, ipi 1mg/kg q 6 weeks, administered until evidence of progression. Patients will be re-imaged by CT between days  $70 \pm 7$  days (Week 9) and evaluated for response.

[figure not shown]

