Immediately discontinue infusion of nivolumab or ipilimumab. Begin an IV infusion of normal saline, and treat the subject as follows. Recommend bronchodilators, epinephrine 0.2 to 1 mg of a 1:1,000 solution for subcutaneous administration or 0.1 to 0.25 mg of a 1:10,000 solution injected slowly for IV administration, and/or diphenhydramine 50 mg IV with methylprednisolone 100 mg IV (or equivalent), as needed. Subject should be monitored until the investigator is comfortable that the symptoms will not recur. Nivolumab or ipilimumab will be permanently discontinued. Investigators should follow their institutional guidelines for the treatment of anaphylaxis. Remain at bedside and monitor subject until recovery from symptoms. In the case of late-occurring hypersensitivity symptoms (e.g., appearance of a localized or generalized pruritus within 1 week after treatment), symptomatic treatment may be given (e.g., oral antihistamine, or corticosteroids).

*The section below is Optional and should be considered if part of assessment criteria. All decisions to continue treatment beyond initial progression documented in the study record and part of an agreement with BMS. Subjects should be re-consented with an ICF describing any reasonably foreseeable risks or discomforts.*

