Treatment Planning: 3D-Conformal or IMRT treatment planning is allowed. This includes "field-in- field" beams as well as the use of dynamic multi-leaf collimator (MLC) derived using inverse planning or electronic compensator techniques. Field arrangements and technique should be chosen that satisfy the PTV dose coverage constraints and normal tissue dose constraints using Dose-Volume Histogram (DVH) analysis. By carefully selecting the gantry and table angle combinations that do not enter or exit through other organs of the body, the dose can be confined to the traditional treatment volumes. Non-coplanar beam arrangements are encouraged, but not required. Dose calculations with tissue inhomogeneity correction must be used. In view of the GI pattern of toxicity of ipilimumab, particular attention will be applied to limit exposure to the bowel. To mitigate this risk, normal tissue constraints of abdominal and pelvic organs will be employed from recommendations from AAPM Task Group 101 (66) and the H. Lee Moffitt Cancer Center experience using this fractionation schedule (67).

After completion of the first course of radiation + ipilimumab at a 3mg/kg dose on Day 1 (or within 24 hours of RT), the patient will start on day 22 the regimen of Nivolumab 360 mg q3 weeks and Ipilimumab 1mg/kg q6 weeks until evidence of progression.

Response assessment will be performed during Day 70 ( $\pm$  7 days) by imaging with PET/CT or CT (CAP).

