**Protocol version 7.0 dated 31DEC2020**

- a. Only for pre-menopausal female patients
- b. SOC labs (COMP, CBC w/diff.).
- c. TSH, T3, T4 required at screening, every 9-12 weeks thereafter while on therapy with ipilimumab and Nivolumab and once a year unless warranted by symptoms or signs detected at follow up visits. May be requested by treating physician if clinically necessary.
- d. 6 Gy X5, daily
- e. Blood for immune monitoring studies will be collected at baseline, end of radiation therapy, at the time of the first three infusions of ipilimumab, at the time of the first three infusions of nivolumab, at response evaluation (day 70), and at 6 month follow up. See Appendix 2 for details.
- f. Ipilimumab infusion 1mg/kg q6 weeks. After Day 70 (+/- 7 days) response assessment, if patients have disease progression, patients will come off study. Patients who demonstrate partial, stable or complete response will continue to receive ipilimumab q6 weeks.
- g. Nivolumab infusion 360mg q 3 weeks. After Day 70 (+/- 7 days) response assessment, if patients have disease progression, patients will come off study. Patients who demonstrate partial, stable or complete response will continue to receive nivolumab q3 weeks.
- h. All Infusions will have a  $\pm$  3 day window
- i. Stool samples will be collected on Day 1, Day 22, and Day 70 and at 6 month follow up. See appendix 11 for details.
- j. Biopsies will be optional and will be obtained at baseline and at day 22.

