#### 14.0 RESPONSE ENDPOINTS

Ipilimumab and Nivolumab are expected to trigger immune-mediated responses, which

require activation of the immune system prior to the observation of clinical responses. Such immune activation may take weeks to months to be evident. Some patients may have objective volume increase of tumor lesions or other disease parameters (based on study indication, i.e., hematologic malignancies) within 12 weeks following start of ipilimumab dosing. Such patients may not have had sufficient time to develop the required immune activation or, in some patients, tumor volume or other disease parameter increases may represent infiltration of lymphocytes into the original tumor or blood. In conventional studies, such tumor volume or relevant laboratory parameter increase during the first 12 weeks of the study would constitute PD and lead to discontinuation of imaging to detect response, thus disregarding the potential for subsequent immune-mediated clinical response.

Therefore, patients with tumor volume increase detected or lack of laboratory parameter response documentation prior to week 12 but without rapid clinical deterioration should continue to be treated with ipilimumab and Nivolumab and clinically observed with a stringent imaging schedule to allow detection of a subsequent tumor response. This will improve the overall assessment of the clinical activity of ipilimumab and Nivolumab and more likely capture its true potential to induce clinical responses. Tumor assessments will be made using modified WHO criteria.

Radiotherapy in the dose and fractionation proposed in this study is a standard palliation tool for metastatic lesions. It is expected that approximately 50% of the irradiated lesions will achieve an objective response (PR+CR). For the purpose of this study, the irradiated lesion will be excluded from baseline measurement and measurement for the assessment of response. In field response will be recorded separately.

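### Progression at the day 70 scan: the calendar footnotes stop treatment, Section 14.0 continues it for tumor growth without rapid decline, and no section says which governs

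*Combined protocol and SAP*

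**What the plan says.** Footnotes f and g in Section 10.0, one for each drug, state that after the day 70 ± 7 assessment, "if patients have disease progression, patients will come off study". Only patients with partial response, stable disease or complete response go on to further doses.

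Three other places fit that rule. The synopsis schema puts dosing and the scan side by side: "administered until evidence of progression. Patients are re-imaged at Week 9". Section 4.0 has the combination "administered until evidence of progression", and Section 8.2 has "Nivolumab 360 mg q3 weeks and Ipilimumab 1mg/kg q6 weeks until evidence of progression".

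Section 14.0 goes the other way. Patients with a tumor volume increase "prior to week 12 but without rapid clinical deterioration should continue to be treated with ipilimumab and Nivolumab" and be "clinically observed with a stringent imaging schedule to allow detection of a subsequent tumor response".

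Treatment Beyond Progression in Section 6.0 would permit dosing past first RECIST 1.1 progression if the investigator sees clinical benefit and the drug is tolerated, until a further 10% increase in tumor burden. The note directly above it reads "The section below is Optional and should be considered if part of assessment criteria". That note also asks for an agreement with the drug supplier and adds: "Subjects should be re-consented with an ICF describing any reasonably foreseeable risks or discomforts".

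**The concern.** A patient whose target lesions have grown enough for progression at the day 70 scan, but who is clinically steady, gets two opposite instructions. Two sites, or two physicians at one site, could each follow the protocol and treat that patient differently.

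Both choices carry a consequence. Continuing prolongs exposure to a combination for which the two arms in Figure 7 show 37% and 33% grade 3–4 treatment-related events, possibly without the re-consent that the Section 6.0 note calls for. Stopping removes the chance of a late response that Section 14.0 is written to protect. If the footnotes are taken at their word and the patient leaves the study, the confirmatory scan and survival data may be lost as well.

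**Working it through.** **1. Do both rules reach the same scan?** The window is 70 − 7 = day 63 to 70 + 7 = day 77. Week 12 is complete at 12 × 7 = day 84, and its first day is 11 × 7 + 1 = day 78. Since 77 < 78, the whole window precedes week 12 on either count. (The response definition in Section 4.0 also mentions CT at 3 months, but footnotes f and g are tied to the day 70 scan.)

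**2. Do both rules reach the same finding?** In part. The footnotes cover any disease progression. Under Section 13.4, that means growth of at least 20% (and 5 mm) in the target sum, a new lesion, or unequivocal non-target progression. Section 14.0 names tumor volume increase or lack of a laboratory response, and says that in conventional studies such an increase would count as progression. The clear overlap is therefore progression by tumor growth without rapid clinical decline. Progression by new or non-target lesions is not named in Section 14.0.

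**3. Does another section break the tie?** No.
- Section 8.5 (off study), Section 12.0 (drug discontinuation) and the Discontinuation Criteria in Section 6.0 do not list progression.
- Treatment Beyond Progression is worded as a working rule, but the optional note stands above it. It still contains a drafting instruction with an example sentence on dating progression. It also mentions four induction doses of ipilimumab, whereas this regimen has one dose at 3 mg/kg.
- Even if that section is in force, it permits continuation where Section 14.0 says patients should continue, and it still contradicts the footnotes.

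**4. Can the decision wait for confirmation?** Section 13.4 asks for a scan 4 weeks after progression: 63 + 28 = day 91 to 77 + 28 = day 105. With nivolumab on time from day 22, the fourth dose is at 22 + 3 × 21 = day 85, with a window of days 82–88. Since 77 < 82 and 88 < 91, that dose falls between the progression scan and its confirmation. This assumes no dose delay, which Section 6.0 allows for drug-related events. No section makes dosing depend on confirmation, so the step shows only that a site on schedule must choose a rule early.

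**5. Off study against follow-up.** Taken literally, the footnotes conflict with:
- the confirmatory scan in Section 13.4;
- the 12-weekly imaging in the calendar's follow-up column;
- the synopsis follow-up of 5 years or until death;
- Section 11.0, which separates leaving treatment from leaving all follow-up;
- overall survival in Section 17.3.

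**6. Is the primary decision touched?** Section 13.4 closes best overall response at progression, so a response after it does not count, whichever dosing rule is followed. For completeness, the stated design reproduces. With continuation at 5 or more of 15 and success at 18 or more of 44, the probability of success is the sum over x = 5 to 15 of P(Bin(15, p) = x) × P(Bin(29, p) ≥ 18 − x). This gives 0.0946 at p = 0.31 and 0.900 at p = 0.51, against the stated 0.10 and 90%. Aligning the dosing text changes neither. (Section 17.2 gives the cut-off as 17; that is a separate matter, and 18 is the value that fits the stated error rates.)

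**The case against.** The best defense is that the parts fit together: treat until progression by default, with Treatment Beyond Progression as the conditional exception and Section 14.0 as its rationale. The footnotes are then shorthand, and because they hang on the two drug rows of the calendar, leaving the study means leaving treatment.

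Much of this has force. Leaving treatment was probably what was meant. A reader might infer that the Section 6.0 exception was rejected, but no text rejects it; its status is open. A reader might also infer that imaging ends at progression, because the 3-monthly scans in Section 13.4 do. Yet the same section requires a confirmatory scan, and the calendar lists 12-weekly imaging in follow-up, so what is missing is only a definition of the stringent schedule. Section 17.3 already ends PFS, time to progression and duration of response at documented progression.

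The defense still does not remove the conflict. It asks sites to treat an optional note as adopted and to set aside an explicit instruction printed twice in the calendar. Nothing in the protocol tells them to do so.

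**Conclusion.** The contradiction stands for a defined group: progression through tumor volume increase at the day 70 ± 7 scan, without rapid clinical decline. It rests on the text and on 77 being earlier than 84, and it needs no outside assumption. The literal conflict between leaving the study and the planned follow-up also stands, as a wording fault.

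Its size cannot be derived, because the protocol gives neither the share of patients progressing at day 70 nor the share of those who are clinically steady. A reader might borrow the 13% and 28% best response of progressive disease in Figure 8. Those arms had neither radiotherapy nor the 3 mg/kg induction, and best response over a whole trial is not progression at day 70, so the figures do not estimate the patients in conflict.

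A reader might also infer that responses after progression could enter the 18 of 44, since Section 13.4 mentions irRC and Section 14.0 modified WHO criteria. The documents do not support that: best response ends at progression, and the primary endpoint is described by RECIST 1.1. No effect on the primary decision is shown. The plan should be corrected because of its effect on dosing, exposure and follow-up.

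**What to change.** 1. Choose one rule for progression at day 70 and make the synopsis, Sections 4.0, 6.0, 8.2 and 14.0 and footnotes f and g agree.
   - *Stop at RECIST 1.1 progression:* delete the continuation sentence in Section 14.0, and the Treatment Beyond Progression section with its note. This adds no visits or scans, but it changes care and needs IRB approval, with provision for any patient already being treated past progression.
   - *Continue under the Section 6.0 criteria:* delete the optional note, add the exception to footnotes f and g, say whether progression by new lesions qualifies, and state the scan schedule after progression. The cost is IRB approval, re-consent, the supplier agreement, and possibly extra scans.
2. Under either option, reword footnotes f and g to: *come off study treatment; confirmatory scan and survival follow-up continue*. Under the second option this applies to patients who do not meet the criteria. It costs one phrase.
3. State in Section 17 that progression is dated at first RECIST 1.1 progression, and that later responses are listed separately and do not count toward 18 of 44. Remove the irRC reference in Section 13.4 and the modified WHO references in Sections 14.0 and 8.4, or label them exploratory. This is text only; it makes explicit what Sections 13.4 and 17.3 already imply.

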## 11.0 PROCEDURES BY VISIT

### Study Completion or Early Discontinuation Visit

At the time of study early withdrawal, the reason for early withdrawal and any new or continuing AEs should be documented. There are two levels of withdrawal and it should be documented whether one or both levels are met. The first level is withdrawal from protocol treatment and testing schedule. The second level is withdrawal from all subsequent follow-up (e.g. disease progression and overall survival). A patient may choose to withdraw from further treatment and protocol assessments but is willing to be followed for disease progression and survival.

## 12.0 STUDY DRUG DISCONTINUATION

- Intercurrent illness that prevents further administration of treatment,
- Unacceptable toxicity (defined in Section 4.3.3.1),
- Patient decides to withdraw from the treatment, or
- General or specific changes in the patient's condition render the patient unacceptable for further treatment in the judgment of the investigator.

## 13.0 DETAILS OF PROCEDURES

### 13.1 Study Materials

Ipilimumab is an FDA approved therapy for metastatic melanoma, and is not FDA approved for NSCLC. Study drug will be provided by BMS, the manufacturer.

The radiotherapy component of this study is a standard procedure for palliation of metastatic NSCLC lesions and will be covered by the patients' insurance.

Patients will not incur costs associated with the study drug.

### 13.2 Safety Assessments

All patients who receive at least one dose of ipilimumab will be considered evaluable for safety parameters. Additionally, any occurrence of a SAE from time of consent forward, up to and including follow-up visits will be reported. Refer to safety reporting Section 6.2

Safety will be evaluated for all treated patients using the NCI CTCAE version 5.0 (<http://ctep.cancer.gov>). Safety assessments will be based on medical review of AE reports and the results of vital sign measurements, physical examinations and clinical laboratory tests.

### 13.3 Cost to Subjects

Each subject or their insurance company will be charged and held responsible for the costs of care provided as part of this study. The study drugs (ipilimumab and nivolumab) will be provided free of charge by BMS. Radiotherapy is a standard treatment for metastatic NSCLC and will be billed to subjects and their insurance companies.

### 13.4 Criteria for Evaluation

#### Safety evaluation

All patients who receive at least one dose of ipilimumab or nivolumab will be considered evaluable for safety parameters. Adverse events will be collected and documented at every visit. Serious Adverse events will be documented and immediately reported to the all concerned authorities as per institutional and sponsor guidelines. This study will be conducted in accordance with the guidelines of the 2001 NCI approved data Safety and Monitoring plan for the WCM Cancer Institute. Reports to the Data Safety and Monitoring Committee will include the following information: accruals, targets, responses, adverse events and evidence of reporting to appropriate review committees.

At the time of protocol initiation the WCM Data and Safety Monitoring Board (DSMB) will review the IRB approved protocol, the data and safety monitoring plan and any stopping guidelines (15.0, page 56). A WCM DSMB data and safety analysis will be performed every six months following the accrual of the first study subject. The WCM DSMB may also convene as needed if stopping criteria are met or other safety issues arise from communications of the Principal Investigator and/or IRB.

